8. STUDY INTERVENTION

8.1 Identity of Investigational Products

There are no investigational products used in this study, as PCT and ultrasound are 2 recognised

diagnostic methods for pneumonia. The trial interventions consist of the UltraPro algorithm (Intervention 1) and of the PCT only arm (Intervention 2).

We did not include an additional arm testing lung ultrasound alone as the PCT rule-in test to decide on lung ultrasonography will decrease the number of patients who need to undergo ultrasound, which is time-consuming and will be easier to implement at large scale in GP practices.

This is a three-arm intervention study (Figure 3):

- Arm 1 (UltraPro): Management based on sequential testing of PCT and lung ultrasonography
- Arm 2 (PCT): Management based on PCT result only
- Arm 3 (control): Usual care

Experimental Intervention (treatment / medical device)

Arm 1: UltraPro

GPs randomly assigned to the UltraPro arm will be responsible to recruit patients fulfilling the inclusion criteria and manage them using the UltraPro algorithm. This is also the arm evaluated during the pilot study.

The UltraPro algorithm combines the result of a PCT point-of-care test with lung ultrasound result to decide on antibiotic prescription. Other inflammatory biomarkers, such as CRP, will not be used in this arm.

GPs in this group will also receive detailed training (described in section 8.2.1) on the epidemiology and management of pneumonia in Switzerland as part of the intervention.

First, PCT will be measured using the portable Thermo-Fisher© PCT Direct rapid point-of-care test provided by the study team. This immunoassay provides a quantitative PCT result in 20 minutes using 20 µL of whole blood. This new device has been validated by comparison with the reference method (Thermo-Fisher, personal communication excellent correlation index, $r^2=0.95$). The PCT threshold to decide on doing a lung ultrasonography has been chosen according to previous reports showing the safety of using a cut-off of 0.25 µg/L to decide on antibiotics prescription in case of acute respiratory infection at primary care level [13, 23, 24].

In case of elevated PCT result ($\geq 0.25 \mu\text{g/L}$), a lung ultrasound will be performed to look for the presence of a lung infiltrate or consolidation suggesting the presence of CAP (Figure 3). Lung ultrasonography using the Phillips© Lumify portable ultrasound with a L12-4 (convex) transducer will be performed. The ultrasound will be provided to the GPs by the study team.

The lung ultrasound will be done following international evidence-based recommendations for point-of-care lung ultrasound using a ten points sonographic technique and the criteria for positive scan and positive examination for the diagnosis of pneumonia [39, 40]. The lung ultrasound is expected to last for 15 minutes.

Antibiotics will be prescribed only if a lung infiltrate or consolidation is identified during lung US. The choice, dosage and duration of antibiotic treatment will be left to the discretion of the GP.

Naso-pharyngeal swabs and venous blood samples will be systematically collected for further exploratory analysis. Sputum will also be collected if the patient is able to produce it.

Arm 2: PCT

GPs randomly assigned to the PCT arm will be responsible to recruit patients fulfilling the inclusion criteria and manage them using the PCT result.

GPs in this group will also receive training detailed training (described in section 8.2.1) on the epidemiology and management of pneumonia in Switzerland as part of the intervention.

The PCT point-of-care test will be performed, as described above, to decide on antibiotic prescription. Antibiotics will be prescribed only in case of elevated PCT ($\geq 0.25 \mu\text{g/L}$) (Figure 3). The choice, dosage and duration of antibiotic treatment will be left to the discretion of the GP.

Naso-pharyngeal swabs and venous blood samples will be systematically collected for further exploratory analysis. Sputum will also be collected if the patient is able to expectorate.

Control Intervention (standard/routine/comparator treatment / medical device)

Arm 3: usual care arm

GPs randomly assigned to the usual care arm will be responsible to recruit patients fulfilling the inclusion criteria and will manage and treat these patients as they usually do (Figure 3). They will not receive any additional training.

Naso-pharyngeal swabs will be systematically collected for further exploratory analysis. Sputum will also be collected if the patient is able to produce it. Venous blood samples will not be collected as blood drawing will not be systematically performed in these patients.

[figure not shown]

Figure 3: Description of the different arms of the study

Packaging, Labelling and Supply (re-supply)

Not applicable

Storage Conditions

Not applicable

8.2 Administration of experimental and control interventions

Experimental Intervention

Arm 1 – UltraPro

A training program for physicians recruited in the UltraPro arm will be performed.

Physicians in arm 1 (UltraPro) will receive detailed training on the epidemiology of pneumonia in Switzerland, international and Swiss guidelines for the management of CAP at primary care level and recent experiences with PCT and ultrasound use to guide antibiotic prescription. They will be sensitized to the issue of antibiotic over-prescription for respiratory infections and resistance development. The rationale for the UltraPro decision tree will be presented.

The objective of the training is to achieve independent lung ultrasound practice and appropriate identification of images compatible with pneumonia. The following topics will be included in the curriculum: basic ultrasound physics, use of ultrasound equipment, probe positioning, images recording and interpretation. An extra 4 hours refresher session in lung ultrasonography is planned for GPs in the UltraPro group, it will be conducted 3-4 months after the start of the study.

Finally, the objective and operating procedures of the study will be presented in detail.

The training curriculum of GPs is described in table 1.

Day	Instructional format	Training content
Morning Day 1	Lecture	
Pre-training test: Questionnaire evaluation of prior knowledge on antibiotic resistance and management of LRTI
 
Description of the objectives of the training
 
Presentation of local epidemiological data on antibiotic resistance, guidelines for the management of LRTI and pneumonia
 
Presentation of the evidence behind our study algorithms
 
Description of the use of PCT POCT
 
Presentation of Good Clinical Practice and of the study procedures

Afternoon Day 1	Lecture	
Overview of the ultrasound training curriculum
 
Presentation of basic ultrasound physics, ultrasound equipment use, the basic eight-region sonographic technique and description of quality criteria for image acquisition.

	Practical testing	
Training in using the standard lung ultrasound procedure.
 
Direct supervision of lung ultrasonography on healthy volunteers to learn image acquisition.

	Workshop in small groups	
Training in images interpretation using lung ultrasound examples of normal imaging and pneumonia characteristics.

	Post-training testing	
Test: Questionnaire on updated general knowledge
 
Test evaluating image acquisition on a healthy volunteer (duration of the exam and quality criteria)
 
Test evaluating image interpretation using existing images
 
Learning objectives: proportion of 95% of good quality images acquisition and 90% of interpretation agreement with the expert
 
In case objectives are not achieved, an extra half-day training will be offered. If the second test evaluation does not reach learning objective, the GP will be excluded of the study.

	Practical training	
Training in using the standard lung ultrasound procedure.
 
Direct supervision of lung ultrasonography on selected cases to improve image acquisition and interpretation.

Table 1: Training curriculum of GPs.

Before starting the study, a face-to-face visit of the GP at his own practice will be done. The medical assistant will be trained in the screening procedure and in PCT measurement.

Arm 2- PCT

A training program for physicians and medical assistants recruited in the PCT arm will be performed.

The training will be the same as described above in table 1 except for lung ultrasonography. GPs will have half day training corresponding to the morning of day 1.

Before starting the study, a face-to-face visit of the GP at his own practice will be done. The medical assistant will be trained in the screening procedure and in PCT measurement.

Control Intervention

Before starting the study, a face-to-face visit of the GP at his own practice will be done. The medical assistant will be trained in the screening procedure and in performing naso-pharyngeal swabs and collecting sputa.

There will be no training program for physicians and medical assistants recruited in the “usual care” arm. This is a deliberate choice as the detailed training on local epidemiological data, antibiotic resistance and guidelines for the management of LRTI and pneumonia is part of the experimental intervention. Giving this training to GPs in the “usual care” could lead to reduced inappropriate antibiotic prescription.

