An individual patient may also choose to refuse the phone interview, without discontinuing the study itself. In this case, the investigators can access the medical file until the end of the 28 days observation period.

There are no foreseeable reasons for investigators to withdraw a patient from the study. Patients who are not reachable during follow-up will not have outcome data. They will be excluded from the analysis of the safety of the intervention but they will still be included in the assessment of impact on antibiotic treatment and of the feasibility of the intervention.

Physicians may choose to discontinue participating in the study. If so, they are responsible of informing the study team. If discontinuation occurs before the training and randomisation session, they will be replaced by another willing physician. If discontinuation occurs after patient recruitment, training and randomisation, patient outcomes will be collected by the study staff until the end of planned follow-up. Access to the medical files will be discussed on a case by case basis with the physician.

There is no foreseeable reason for the investigators to withdraw a physician from the study once he participated in patient recruitment, training and randomisation.

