11.4 Planned Analyses

Datasets to be analysed, analysis populations

The analysis will be performed in intention to treat (pragmatic trial). The analysis population will comprise all patients included by the randomised GPs. The primary analysis will include all patients enrolled in the study, irrespective of follow-up. Patients who are lost to follow-up will be considered as having had a clinical failure, an adverse outcome and duration of disease equal to the maximum duration measured in the other patients. Patients in whom GPs did not follow the respective algorithm recommendation and/or who did not have complete telephone follow-up will be excluded from the per-protocol analysis.

Primary Analysis

Odds ratio of antibiotic prescription between 2 groups as well as the difference in proportion of patients prescribed an antibiotic by day 28 using logistic regression corrected for variation at the GP level (generalized linear mixed effect)

Secondary Analyses

The following statistical analyses are planned:

- Difference between the mean number of days with restricted activities by day 14 using linear mixed effect regression
- Difference between the mean number of medical consultations by day 28 using linear mixed effect regression
- Odds ratio of adverse outcome between 2 groups as well as the difference in proportion of patients with adverse outcome and clinical failure using logistic regression corrected for variation at the GP level (generalized linear mixed effect)
- Difference between the mean daily symptom scores measured in the different arms. The effects of the interventions on recovery will be studied by comparing the slopes of symptom scores over time between arms
- Difference in the mean duration of total time spent in the practice using linear mixed effect regression
- Difference in levels of satisfaction of providers and of patients between arms
- Difference in the mean cost per arm using linear mixed effect regression
- Diagnostic performance of:
 - individual host biomarker(s) based on crude positive and negative likelihood ratios, and on the area under the curve of receiver operator characteristic (ROC) curves, to predict the development of a life-threatening disease, clinical failure, or the presence of pneumonia (using a clinical diagnosis).

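### GPs who fail the ultrasound test twice are excluded in the UltraPro arm only, by inference after allocation, and the analysis set would not show the lost clusters

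*Combined protocol and SAP*

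**What the plan says.** Section 8.2 opens the arm 1 description with "A training program for physicians recruited in the UltraPro arm will be performed". Table 1 ends that training with a test whose pass mark is a "proportion of 95% of good quality images acquisition and 90% of interpretation agreement with the expert". A GP who misses it is offered an extra half day. After that, "If the second test evaluation does not reach learning objective, the GP will be excluded of the study".

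The other arms face no such test. For the PCT arm, "The training will be the same as described above in table 1 except for lung ultrasonography". For usual care, "There will be no training program for physicians and medical assistants recruited in the" control arm.

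Section 7.2, on withdrawal, provides for early departures: "If discontinuation occurs before the training and randomisation session, they will be replaced by another willing physician". It then adds: "There is no foreseeable reason for the investigators to withdraw a physician from the study once he participated in patient recruitment, training and randomisation".

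Section 11.4 declares an intention-to-treat analysis and defines the set: "The analysis population will comprise all patients included by the randomised GPs".

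No section says whether a GP excluded at the test is replaced, reported or counted.

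**The concern.** The GP is the unit of randomisation. A rule that removes GPs from one arm for poor performance after allocation replaces a randomised group of GPs with a selected one. UltraPro would then consist of GPs who passed a demanding test, while the PCT and usual-care arms keep every kind of GP. If the ability to pass goes with prescribing habits or with adherence to an algorithm, the UltraPro v PCT and UltraPro v usual-care contrasts mix the effect of the algorithm with the effect of the selection. PCT v usual care is untouched.

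The planned mixed model does not help. It describes variation among the GPs who are present and cannot restore a cluster that was never observed. Replacing a failed GP would restore the numbers but not the comparability, because the replacement must pass the same test.

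The trial is also presented as pragmatic and as a guide to wider implementation, and GPs who struggle with ultrasound are part of that question.

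**Working it through.** **1. Order of allocation and test.** Section 8.1 speaks of GPs randomly assigned to UltraPro and says that this group receives the training described in section 8.2. The ultrasound part is given in no other arm, so a GP must already be allocated when sitting the test. No sentence states this order, and section 7.2 refers to training and randomisation as one session. The order is therefore an inference, though a strong one.

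**2. One arm only.** Usual-care GPs have no training. PCT GPs attend only the first morning, without ultrasound. Exclusion on this test can happen only in UltraPro.

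**3. Fate of the cluster.** Section 7.2 allows replacement before the training and randomisation session, and follows up patients when a GP leaves after recruiting. A GP who fails the test falls between the two rules. That GP has presumably recruited nobody, so the section 11.4 set contains no patient from the cluster and the loss is invisible.

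**4. Size of a possible bias.** Inputs: 14 GPs per arm with 15 patients each, and a target difference of 15 points (section 11.2). Let the retained UltraPro GPs prescribe at rate p, and let k excluded GPs differ from them by d. The rate over all 14 randomised GPs is

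[(14 − k)p + k(p + d)] / 14 = p + (k/14)d,

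so the shift is (k/14)d. The documents give neither k nor d; the values below are assumptions.

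| k | d = 0 | d = ±10 points | d = ±30 points |
|---|---|---|---|
| 1 | 0 | ±0.7 | ±2.1 |
| 2 | 0 | ±1.4 | ±4.3 |
| 3 | 0 | ±2.1 | ±6.4 |

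Relative to the target, 0.7/15 is about 5% and 6.4/15 about 43%. With d positive, the observed UltraPro rate is too low and its benefit is overstated; with d negative, the reverse holds.

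**5. Power.** The plan states 80% at intracluster coefficient 0.06. With the usual design effect, 1 + (15 − 1) × 0.06 = 1.84, the effective size is 210/1.84 = 114 per arm. Normal-approximation power for 45% v 30%, two-sided 5%, is then 65.0%, so the stated figure is not reproduced on that reading. If 0.06 is instead a variance on the logit scale (coefficient about 0.014), power is 83.0%. The simulation figure is not shown, so the intended meaning cannot be confirmed. That is a separate matter; only the change per lost GP matters here, with 14 PCT GPs retained.

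| UltraPro GPs | Power, coefficient 0.06 | Power, coefficient 0.014 |
|---|---|---|
| 14 | 65.0% | 83.0% |
| 13 | 63.3% | 81.5% |
| 12 | 61.3% | 79.8% |
| 11 | 59.1% | 77.8% |

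Three lost GPs cost 65.0 − 59.1 = 5.9 points or 83.0 − 77.8 = 5.2 points. The first lost GP costs less than 2 points on either reading.

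**The case against.** Three stronger readings are tempting, and the documents support none of them.

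- A reader might infer that Table 1 flatly contradicts section 7.2. That passage is not a rule against withdrawing randomised physicians. It is a statement that no reason is foreseen, and it applies once a GP has taken part in recruitment, training and randomisation. A GP who fails the test has presumably not recruited. What stands is a tension: Table 1 does foresee a reason for removing a GP who has been trained and, by inference, randomised.
- A reader might infer that the stated intention-to-treat set is violated. It is not, because no enrolled patient is dropped. The weakness is that a set defined by included patients cannot register a randomised GP who includes none.
- A reader might infer that UltraPro will look better than it is. The documents offer no link between an imaging test and prescribing, so zero bias and bias in the other direction are equally compatible with them.

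It can also be said that failure after remedial training may be rare, and that the pilot measures how many GPs meet the training objectives. That is fair, but the pilot trains only four GPs. Even with no failures among them, a true failure rate of up to 1 − 0.05^(1/4) = 53% would not be ruled out at the one-sided 5% level.

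The weightiest objection is that a competence test may protect patients, because section 3.4 names inappropriate withholding of antibiotics in pneumonia as a risk. This stands. It bears on how such a GP's patients are managed, and that can be decided separately from whether the cluster stays in the trial's data.

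**Conclusion.** The point holds as a conditional risk of selection bias in the two UltraPro contrasts, created by a stated rule and hidden by the definition of the analysis set. It needs at least one GP to fail twice and failure to be related to prescribing; otherwise the bias is zero. Under the assumed range of 1 to 3 GPs and 10 to 30 points, the UltraPro rate shifts by 0.7 to 6.4 points in either direction, against a target of 15. The loss of power is secondary. The conclusion rests on the inference that allocation precedes the test, and on an excluded GP enrolling nobody. It should be settled before any GP is dropped, since a cluster that was never observed cannot be recovered in the analysis.

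**What to change.** Reconcile sections 7.2, 8.2 (Table 1) and 11.4 as follows.

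1. State the order of randomisation, training and testing, and whether a GP lost after allocation may be replaced.
2. Provide that a GP who fails the test is not removed from data collection. The practice goes on screening, seeking consent and recording prescriptions and follow-up. Its patients are analysed in UltraPro under intention to treat and left out of the per-protocol set. This matches how sections 8.3 and 11.4 already treat departures from the algorithm.
3. Leave to the clinical team whether that GP uses ultrasound and how the patients are managed. Nothing is proposed here on that, but the three sections must agree with the decision.
4. Report by arm the number of GPs randomised, failing the test (UltraPro only) and lost.
5. If a cluster is still lost, add a sensitivity analysis that recomputes the UltraPro rate as [(14 − k) × observed rate + k × assumed rate]/14 (14 being the planned number of GPs). The assumed rates should run above and below the observed one and include no difference. Screening records cannot replace this, because a practice that never started has none.

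The cost is a protocol amendment, continued data collection in any such practice, and some dilution of the UltraPro effect.

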8.3 Intervention modifications

The GPs may modify the allocated intervention or administer components of the intervention at time points not specified beforehand.

The proportion of modification of the intervention in each intervention arm will be recorded. The adherence to the treatment recommendations resulting from pre-defined patient management will be recorded. Data will be used for the intention to treat analysis.

Such findings will inform us on the feasibility and scalability of the study on a larger scale.

8.4 Compliance with study intervention

Full completion of the eCRF will enhance compliance with the intervention. The training programme as described above will also enhance adherence to the study intervention.

8.5 Data Collection and Follow-up for withdrawn participants

Pilot Study

All study participants recruited in the pilot study will have their data collected per the protocol detailed below. Such data will not be used for the final analysis of the study results but to streamline study procedures to facilitate the execution of the randomized trial.

Additional qualitative and quantitative data relating to the barriers and facilitators to the implementation of the study will be collected.

Qualitative data

The following methods will be used to obtain qualitative data on the general feasibility of the randomized trial in the proposed setting.

Observation

Two consultations will be observed: one at the *Permanence* of the PMU and one in the setting of a general practice. The observation will be performed in a non-participative way by one of the investigators. Data regarding the study process and material hurdles to the correct execution of the algorithm will be produced using a pre-defined observation chart.

Interviews

Semi-structured interviews, using a pre-defined interview guide, will be conducted by one of the investigators with three of the participating GPs in the practice.

Interviews will be done after the end of the pilot study so that he can reflect on the practical experience gained.

Interviews will be recorded using standard equipment and transcription will be outsourced.

First, transcripts will be read to identify abstract themes relating to the meaning of the text. After the identification of the main themes, these will be developed in a coding scheme that will be applied to the text. The codes will then be applied in an independent fashion by two different investigators. Software designed for qualitative analysis (QDA Miner© or Atlas.ti©) will be used. This will allow for an analysis and interpretation of the meaning of the text. The overall objective is to identify barriers and facilitators to the implementation and to the execution of the UltraPro algorithm for the randomized study.

Focus groups

One focus group comprising of medical assistants working at the walk-in centre will be done by two of

the study investigators. The aim is to produce data regarding eventual barriers to implementing procedures in the randomized trial and to further identify barriers and facilitators to the wider execution of the study.

The focus group will be recorded using standard equipment and transcription will be outsourced...

Transcripts will be read to identify abstract themes relating to the meaning of the text. After the identification of the main themes, these will be developed in a coding scheme that will be applied to the text. The codes will then be applied to the text of in an independent fashion by two different investigators. Software designed for qualitative analysis (QDA Miner[©] or Atlas.ti[©]) will be used.

Quantitative data

Quantitative data relating to the study processes will be obtained by questionnaires designed to assess different steps of the study process.

Clinical data will be collected as per protocol for the randomized trial

Randomized trial

All study participants will undergo clinical and laboratory evaluation at inclusion (Day 0) according to the arm to which they are allocated. The following data will be collected:

Clinical data collection

A short electronic case report form (eCRF) will be filled by the GP on a tablet computer provided by the study team. Data collected include demographic characteristics, medical history, symptoms and clinical examination findings. Whether or not the GP ordered supplementary tests for the management of the patient outside the scope the algorithm will be recorded.

Ultrasonographic (UltraPro arm) data collection

All US images captured will be digitally recorded and transferred via a secured internet connection along with relevant metadata to a secure server. For study quality control purposes, the quality of the image and the interpretation of a random sample of images will be evaluated retrospectively by an experienced radiologist.

Laboratory specimen collection

Blood samples

In the UltraPro and PCT arms, a total of 17.5 mL of whole venous blood will be drawn to perform the PCT POCT measurement and for the exploratory objectives.

50 µL of whole blood will be used for the POCT PCT measurement. The rest of the sample will be used for identification of novel host biomarkers and genetic (identification of SNPs in genes that regulate microvascular integrity and transcriptomics) analyses that will be done in batch after the completion of the study. This will be performed at the Sandra Rotman Laboratory in Ontario, Canada

The following table describes the nature of the biological sampling:

Tube	Volume	Storage	Aim
EDTA 7.5 ml	20µL of whole blood	None	POCT PCT measurement
	3 x 1000 µL of whole blood	-80°C	SNPs analysis Biobank
EDTA 7.5 ml	3 x 1000 µL of plasma	-80°C	Novel host biomarkers Biobank
PaxGene	2.5 ml	-80°C	Transcriptomics

Table 2. Details of blood samples collected in the study

Naso-pharyngeal swabs

For future analyses, a naso-pharyngeal swab will be performed on all patients recruited in the study. A eSwab™ (Copan Diagnostics[©]) will be introduced in the nasal cavity until the naso-pharynx in one

nostrils. Swabbing will then be performed. The sample will then be conserved at -80°C using a liquid collection and transportation system.

A respiratory pathogen multiplex real time polymerase chain reaction (PCR) assay will be retrospectively performed in the laboratory of virology of Geneva University Hospital to identify the aetiological agent of the LRTI. Such an approach has been described in other studies [41].

Sputa

For future analyses, a sputum sample will be collected for all patients recruited in the study if they are able to produce it. The sample will then be conserved at -80°C.

A respiratory pathogen multiplex real time PCR assay will be retrospectively performed in the laboratory of virology of Geneva University Hospital and culture will be performed in the microbiology laboratory of Lausanne University Hospital to identify the aetiological agent of the LRTI.

Follow-up after initial assessment

Active surveillance

All participants will be contacted by phone at day 7 and day 28 by the study team.

At days 7 and 28, a standardized interview will be done to ensure that the patient is alive, to:

- evaluate clinical outcome (presence or recurrence of LRTIs symptoms)
- record any additional visits
- record additional antibiotic prescription
- record number of days during which daily activities (work or recreation) were restricted
- evaluate antibiotic side effects
- record secondary hospital admission
- patient satisfaction will be recorded at day 28 only

The caller will be blinded as to the arm in which the patient was included.

All participants will be asked to fill a daily diary until symptom resolution up to day 28. The diary can be filled in paper and returned by post or for participants who prefer an electronic version will be made available.

They will report each day on 6 items:

- coughing
- phlegm
- shortness of breath
- sleep disturbance
- impairment of normal daily activities
- generally feeling unwell

The variables will be scored on a Likert scale of 0 to 6 (0 = normal, 1 = very little problem, 2 = slight problem, 3 = moderately bad, 4 = bad, 5 = very bad, 6 = as bad as it could be). The use of such a diary has been validated for use in a randomized controlled trial on management of LRTI in primary care [42].

Scores for each of the individual items on symptoms will be added to create a total daily symptom score. The effect of the intervention will be assessed as the difference in the slope of symptom scores over time in the different groups.

Passive surveillance

In case a follow-up visit is planned by the GP, the same algorithm used in their study arm should be applied again to decide on antibiotic prescription, if antibiotics had not been previously prescribed and the GP is willing to prescribe antibiotics.

In case of deterioration, patients will be instructed to come back to the same GP for a follow-up visit if possible. The same algorithm will be used for their management as long as no referral to hospital is needed. A short eCRF will be filled by the GP reporting relevant clinical symptoms and signs as well as the management decision (antibiotic prescription, admission).

